**Table 7 Vital signs reference ranges**

Parameter	Standard Unit	Lower Limit	Upper Limit
Diastolic Blood Pressure	mmHg	60	120
Systolic Blood Pressure	mmHg	100	160
Pulse Rate	Beats/min	40	120
Respiratory Rate	Breaths/Min	8	28
Body Temperature	Celsius	36.5	38
Weight	kg	35	200

Physical examinations (complete or brief), including height (only at baseline) and weight, will be conducted in accordance with the schedule provided in CSP Table 2. Any new findings or aggravated existing abnormalities, judged as clinically significant by the Investigator, will be reported as an AE as described in CSP Section 8.3.5.

The complete physical examination will include an assessment of the following: general appearance, skin, head and neck (including eyes, ears, nose, mouth, and throat), lymph nodes, abdomen, musculoskeletal (including spine and extremities), cardiovascular, respiratory, and neurological systems.

The brief physical examination will include an assessment of the general appearance, abdomen, cardiovascular, and respiratory system. For the brief physical examination, only information on whether the assessment was performed or not is to be recorded.

### **3.5 Tertiary/exploratory outcome variables**

#### **3.5.1 Patient Global Impression of Severity (PGI-S)**

[figure not shown]
Patient Global Impression of Severity (PGI-S) is a single item designed to capture the participant's perception of overall symptom severity over the past 7 days, using a 6-point categorical response scale (no symptoms, very mild, mild, moderate, severe, very severe).

The responses will be scored from 0 = no symptoms to 5 = very severe. Missing responses will not be imputed.

[figure not shown]
The PGI-S is collected at site at Visits 1 and 2 and at home every  $7 \pm 3$  days after Visit 2.

The change from baseline in PGI-S score will be analysed at Week 12, Week 24 and at Week 52 after the extension period.

[figure not shown]
CCI

CCI

CCI

### **3.5.5 European Quality of Life-5 Dimensions (EQ-5D-5L)**

The European Quality of Life-5 Dimensions (EQ-5D-5L) will be analysed separately and not form part of this SAP.

### **3.5.6 CSU-related healthcare resource utilisation**

CSU-related healthcare resource utilisation will be analysed separately and not form part of this SAP.

## **4 ANALYSIS METHODS**

The primary DBL is targeted to occur when all participants have completed the 24-week double-blind treatment period. The final DBL will occur when all participants have completed the 52-week treatment period and the Week 60 follow-up visit and/or the IPD/EOT visit.

All personnel involved in the analyses of the study will remain blinded until the primary DBL and protocol deviations are identified.

The CSR will be based on the final DBL.

## 4.1 General principles

The primary efficacy analyses will be based on the double-blind, 12-week placebo-controlled induction period, including data up to Week 24. Efficacy endpoints will be analysed using the FAS, the analysis of safety endpoints will be based on the safety analysis set. Analysis sets are defined in Section [2](#).

Summary data will be presented in tabular format by treatment group. Categorical data will be summarised using frequency and percentages, where the denominator for calculation is the underlying analysis set population unless otherwise stated. Continuous data will be summarised with descriptive statistics of number of available observations, mean, standard deviation (SD), median, minimum and maximum, and quartiles where more appropriate. Data listings will be sorted by treatment and participant number.

All point estimates will be presented together with 95% confidence intervals (CIs) as measures of precision and nominal 2-sided p-values, rounded to 4 decimal places.

The primary estimand, analysed using the treatment-policy strategy, is the difference in mean change from baseline at Week 12 in ISS7 between each benralizumab dose and placebo, using the full analysis set, including all data up to week 12 regardless of discontinuation of IP or whether use of rescue medication has or has not occurred. As all participants who prematurely discontinue from IP in the study are asked to come in for all visits and study assessments up to Week 52, the amount of missing data expected in the analysis is assumed to be low and this estimand strategy is considered appropriate. However, sensitivity analyses may be performed to assess the robustness of the efficacy results to the missing data assumptions as described in [Appendix 8.1](#).

As described above, in general analyses will follow an ITT principle; while changes to background medications for CSU and related treatments are discouraged, if any do occur, data following any changes to background therapies, or post missed doses or discontinuation of IP will still be included in the analyses. However, sensitivity analyses may be performed to assess any impact of changes in study and background medications if deemed appropriate (see Section [4.2.6.3](#) and [Appendix 8.1](#)).

All analyses across the 24-week double-blind period will include 3 treatment groups comprising, respectively, all participants randomised to benraliuzmab 60 mg initial dose (n=60), all participants randomised to benraliuzmab 30 mg initial dose (n=60) and all participants randomised to placebo initial dose (n=40).

For Week 52 analyses, data over the entire 52-week treatment period will be presented in summaries and data listings with the 5 individual treatment groups to initial dose and maintenance regimen. If it is suitable to pool the data across the initial dose groups to enable one comparison of Q4W versus Q8W with 60 participants per arm, then the model will

include 3 treatment groups (those randomised to benralizumab then Q4W maintenance, those randomised to benralizumab then Q8W maintenance and those randomised to placebo followed by benralizumab treatment). If pooling of treatment groups for Q4W versus Q8W dosing is deemed not appropriate, then the model will include the 5 individual treatment groups to initial dose and maintenance regimen.

Key efficacy tables will also summarise data from start of benralizumab, key safety tables will be produced from start of benralizumab to explore changes from starting active study medication.

The data analyses will be conducted using the SAS® System (SAS Institute Inc., Cary, NC). All SAS® programs used to generate analytical results will be developed and validated according to AstraZeneca SAS® programming standards and validation procedures.

**Table 10 Primary and key secondary efficacy and main safety estimands**

Statistical Category	Estimand 	Section
	Treatment Condition 	
	Endpoint (Population)	
	Intercurrent Event Strategy 	
	Population Level Summary  (Analysis)	
Primary	Treatment with benralizumab versus placebo, regardless of compliance, regardless of rescue medication	
Primary Objective: To determine the clinical efficacy of benralizumab compared to placebo in patients with CSU who are symptomatic despite the use of H1 antihistamine treatment
 
 
• Change from baseline in ISS7 at Week 12 (FAS)
 
• All data up to Week 12 will be included 
 
• Treatment discontinuation – treatment policy
 
• Rescue medication – treatment policy
 
 
 
 
Key secondary Objective: To evaluate the effect of benralizumab compared to placebo on supportive measures of clinical efficacy in patients with CSU who are symptomatic despite the use of H1 antihistamine treatment
 
 
• Change from baseline in UAS7 at Week 12 (FAS)
 
• All data up to Week 12 will be included 
 
• Treatment discontinuation – treatment policy
 
• Rescue medication – treatment policy
 
 
 
 
Safety Objective: To assess the safety and tolerability of benralizumab in patients with CSU who are symptomatic despite the use of H1 antihistamine treatment

Key secondary	Treatment with benralizumab versus placebo, regardless of compliance, regardless of rescue medication	
 
• Difference in least squares mean change from baseline in ISS7 at Week 12 between benralizumab and placebo (MMRM)
 
 
• Difference in least squares mean change from baseline in UAS7 at Week 12 between benralizumab and placebo (MMRM)

Safety	Treatment with benralizumab versus placebo, regardless of compliance, regardless of rescue medication	
 
• AEs
 
• SAEs
 
• Vital Signs
 
• Physical examination (Safety)
 
 
• Remained adherent to intervention (on-treatment)

		4.2.8

 All estimand attributes explicitly identified for primary and key secondary estimands only.

#### **4.1.1 Testing strategy to account for multiplicity considerations**

To control the overall type I error rate to be  $\leq 0.05$  for the multiple comparisons in the primary and the key secondary endpoints, a Multiple Testing Procedure (MTP) with Bonferroni-Holm over groups, and Fixed-Sequence within groups will be applied.

Specifically, there will be 2 groups defined by the doses of 30 and 60 mg, and within each group there will be a pre-defined fixed-sequence MTP of comparisons of the primary and key secondary endpoints versus placebo (ie, change from baseline in ISS7 at Week 12, then change from baseline in UAS7 at Week 12) at level of  $\alpha/2$ .

If the null hypotheses for 1 dose group can be rejected entirely (ie, significant difference between active versus placebo for both endpoints at  $\alpha=0.025$ ), one will increase the level to  $\alpha$  (ie, 0.05) for the other group. This amounts to using Bonferroni-Holm over groups, and fixed-sequence within groups. This multiplicity adjustment method follows the general results described by Bretz ([Bretz et al 2009](#)) and by Burman ([Burman et al 2009](#)).

### **4.2 Analysis methods**

#### **4.2.1 Participant disposition**

Participant disposition will be summarised using the all participants analysis set. The total number of participants will be summarised for the following groups: those who enrolled, those who entered run-in, and those who were not randomised (and reason). The number and percentage of participants within each treatment group will be presented by the following categories: randomised, received treatment with study drug, did not receive treatment with study drug (and reason), completed treatment with study drug, discontinued treatment with study drug (and reason), discontinued treatment with study drug but completed study follow-up, completed treatment, and withdrawn from study (and reason). This will be presented for both, the placebo-controlled treatment period and the extension period.

Screen failure information will be listed for the all participants analysis set.

The number of participants remaining on treatment, participants discontinued IP but still in study follow-up, and participants who withdraw from the study will be summarised by treatment group and scheduled visit, separately for participants in the FAS.

The number of participants randomised by country and centre will also be summarised by treatment group in the FAS.

#### **4.2.2 Demography data and participant characteristics**

Demography and baseline characteristics will be summarised by treatment group and overall in the FAS, using frequency and percentages (for categorical variables) and descriptive statistics of n, mean, standard deviation, median, minimum, and maximum, and where

appropriate 1st quartile (Q1) and 3rd quartile (Q3) (for continuous variables). If there are major differences in the number of participants between the FAS and safety analysis set, these summaries will be repeated for the safety analysis set. These summaries will be presented for reporting of the placebo-controlled treatment period at primary database lock.

Age will be derived from the date of informed consent-date of birth, rounded down to the nearest integer. For participants in countries where date of birth is not recorded, the age as recorded in the electronic case report form (eCRF) will be used.

Various baseline characteristics will also be summarised, including participant characteristics (age (as continuous and categorical variable in 3 categories: <50 years /  $\geq$ 50 to <65 years /  $\geq$  65 years), weight, height, BMI, ethnicity, race, region (randomisation stratification variable)). Medical and surgical histories will be summarised separately for past and current conditions.

#### **4.2.3 Prior and concomitant medications**

The frequency and percentage of participants reporting usage of prior medications, those reporting use of allowed concomitant medications, and those reporting usage of disallowed concomitant medications (refer to Section 6.5 of the CSP) will be summarised by treatment group and overall. Background medications (e.g. type of antihistamine) will be summarised by treatment group and overall.

The summary tables will present data by generic term within ATC code.

The frequency and percentage of participants reporting usage of rescue medication (taken, not taken) over the past 7 days will be summarised by treatment group and overall for scheduled visits. The frequency and percentage of recorded multiple of licensed dose of antihistamine taken each day over the past 7 days will be summarised by treatment group and overall for scheduled visits.

#### **4.2.4 Study treatments**

Exposure to investigational product administration will be calculated in days as:

$$(last\ dose\ date\ of\ IP - first\ dose\ date\ of\ IP + 1)$$

and will be summarised descriptively by treatment group for the safety analysis set.

The number and percentage of participants with duration of IP administration in each of the following categories will also be summarised:

- <12 weeks
- $\geq$ 12 weeks and <20 weeks
- $\geq$ 20 weeks and <36 weeks

- $\geq 36$  weeks and  $< 52$  weeks
- $\geq 52$  weeks.

#### 4.2.5 Compliance

Study treatment compliance with IP administration will be summarised descriptively by treatment group for the FAS and calculated as:

$$(\text{Total doses administered} / \text{total doses expected}) \times 100.$$

The total number of doses expected includes all visits with protocol scheduled IP administration on or before a participant's IP discontinuation or treatment completion date.

#### 4.2.6 Primary outcome variable

##### 4.2.6.1 Primary analysis

For the primary endpoint, change from baseline in ISS7 score to Week 12, for each dose of benralizumab the null hypothesis ( $H_0$ ) is that the change in ISS7 at Week 12 on benralizumab is equal to the change in ISS7 at Week 12 on placebo. The alternative hypothesis is that the change in ISS7 with benralizumab treatment is not equal to the change in ISS7 for placebo:

- $H_0$ : Change from baseline ISS7 at Week 12 (benralizumab 60 mg – Placebo) = 0
- $H_1$ : Change from baseline ISS7 at Week 12 (benralizumab 60 mg – Placebo)  $\neq$  0
- $H_0$ : Change from baseline ISS7 at Week 12 (benralizumab 30 mg – Placebo) = 0
- $H_1$ : Change from baseline ISS7 at Week 12 (benralizumab 30 mg – Placebo)  $\neq$  0

Hypothesis testing for the primary analyses will be performed according to the multiple testing procedure described in Section 4.1.1. If the p-value is less than 0.025 (or 0.05 if alpha can be recycled from the other dose group), the null hypothesis ( $H_0$ ) will be rejected and the alternative hypothesis ( $H_1$ ) will be accepted.

The change from baseline in ISS7 score at Week 12, will be compared between each benralizumab initial treatment group (60 mg and 30 mg) with placebo using a mixed-effect model repeated measurements (MMRM) analysis. The dependent variable in this model will be the change from baseline in ISS7 at post-baseline protocol-specified visits (data included up to the Week 24 visit). Treatment group will be included as an explanatory variable along with the baseline ISS7 score, region, visit and treatment-by-visit interaction as fixed effects. An unstructured covariance structure will be used to model the within-participant errors. If the model fails to converge, the following structures will be attempted in the specified order: Toeplitz, first-order autoregressive, compound symmetric, and variance components.

Results will be presented in terms of least square means (LSMEANS), treatment differences in LSMEANS, 95% CI and p-values for all scheduled visits. The results at Week 12 will be of primary interest. The LSMEANS will be calculated using the OM option in the LSMEANS

statement and the treatment-by-visit interaction to provide an LSMEAN estimate for each scheduled visit. The LSMEANS with 95% CIs will also be presented for each treatment group by scheduled visit.

The missing at random assumption for the analysis is considered appropriate and justified as the primary estimand includes all data collected up to Week 24 in the analysis regardless of discontinuation of randomised treatment, as described in CSP Section 9.4.1, and so the amount of missing data is expected to be low and is considered not likely to impact the primary results.

Sensitivity analyses to alternative missing data assumptions may be performed as described in Section 4.2.6.3 below.

Descriptive summary statistics for scores and change from baseline in ISS7 will be produced by treatment group and visit.

#### **4.2.6.2 Subgroup analyses for the primary outcome variable**

To explore the uniformity of the detected overall treatment effect on the primary efficacy variable, subgroup analyses and statistical modelling including testing for interaction between treatment and covariates will be performed for the following factors:

- Region (Europe, North America, Rest of World; as used in randomisation),
- Gender (male, female),
- Age group categories ( $<65$ ,  $\geq 65$  years),
- BMI ( $\leq 30 \text{ kg/m}^2$ ,  $> 30 \text{ kg/m}^2$ )
- Race (White, Asian, Other),
- Thyroid function defined by TSH (normal thyroid function, low thyroid function),
- Antihistamine use prior to study entry (labelled dose of H1 antihistamine, higher than labelled dose/combination treatment),
- Baseline ISS7 ( $<13$ ,  $\geq 13$ ),
- Baseline UAS7 ( $<\text{median}$ ,  $\geq\text{median}$ ),
- Baseline HSS7 ( $<\text{median}$ ,  $\geq\text{median}$ ),
- Screening period hives over last 7 days (any days without hives, hives on all 7 days; *categories to be confirmed prior to unblinding*),
- Duration of CSU at enrolment ( $<2$ , 2-10,  $>10$  years),
- Prior omalizumab use (Omalizumab naïve, Omalizumab failure, Omalizumab prior responder),
- Angioedema at baseline (presence, absence),
- Baseline blood eosinophils ( $<\text{median}$ ,  $\geq\text{median}$ ),
- BHRA status (BHRA+, BHRA-; *if suitable data will be available*).

Low thyroid function is defined as TSH above normal range or participants taking thyroid supplement.

For each of the subgroup factors in turn, a separate MMRM model will be fitted using the same model terms as used for the primary analysis (described in Section 4.2.6.1), with additional terms for the subgroup main effect and the treatment by subgroup interaction.

Region and baseline ISS7, respectively, will not be a covariate when used as subgroup. If any model does not converge, respective sub-groups may be collapsed appropriately.

Similar outputs will be presented for each subgroup as for the primary analysis. The p-value for the interaction term by each treatment group will be presented in the analysis summary tables and forest plots will present the difference in lsmeans with confidence intervals for each level of the subgroups.

It is important to note that the study has not been designed or powered to assess efficacy within any of these pre-defined subgroups, and as such these analyses are considered as exploratory.

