## **1.2 Number of participants**

Approximately 240 participants will be enrolled/screened in order to achieve 160 eligible study participants randomly assigned to study intervention.

Up to Week 24, ie, prior to start of the extension period evaluating Q4W and Q8W dosing regimens, participants in both benralizumab 60 mg initial dose treatment arms will be considered as a single treatment group (total n=60), as will participants in both benralizumab 30 mg initial dose treatment arms (total n=60). Together with the 40 participants in the placebo treatment arm the above randomisation will provide a 3:3:2 ratio across the treatment group to assess the primary endpoint at Week 12.

This provides 90% power for statistical significance at the 2-sided 2.5% level within each induction dose comparison versus placebo if the assumed effect is a 4.7 point mean difference in change in ISS7 between benralizumab and placebo, assuming a SD of 6 for the change in ISS7 and a 10% dropout rate. These assumptions are in line with those for previous CSU trials ([Saini et al 2015](#)). The proposed sample size also provides a robust dataset to assess the key secondary endpoints, assess potential responders in sub-populations, and make a comparative assessment of the Q4W and Q8W dosing regimens in the maintenance period.

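### The baseline ISS7 subgroup model drops the baseline score and keeps only the <13 / ≥13 split, at a small cost in precision and consistency

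*SAP*

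**What the plan says.** The primary MMRM in SAP 4.2.6.1 adjusts for baseline: "Treatment group will be included as an explanatory variable along with the baseline ISS7 score, region, visit and treatment-by-visit interaction as fixed effects". SAP 4.2.6.2 lists 16 subgroup factors. For each one, "a separate MMRM model will be fitted using the same model terms as used for the primary analysis", with the subgroup main effect and the treatment-by-subgroup interaction added. It then states that "Region and baseline ISS7, respectively, will not be a covariate when used as subgroup".

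The baseline ISS7 factor has two levels, below 13 and 13 or above. In that model, baseline ISS7 therefore enters only as the split. No other section of the SAP or protocol puts the score back. The SAP does not call the covariate continuous, but that is the natural reading of a baseline score entered as a fixed effect.

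The same section says the trial was not designed or powered for these subgroups and treats them as exploratory. Randomisation is stratified by region only (Protocol 6.3.1).

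**The concern.** The exception treats two unlike cases alike. The region subgroup is the very factor used in randomisation and in the primary model, so carrying it twice would be redundant. The ISS7 subgroup is a coarse version of its covariate. Eligible participants have a baseline ISS7 of at least 8 (Protocol 5.1, criterion 5a) and the scale stops at 21 (SAP 3.2), so there is real spread on each side of 13. The outcome is change from that same baseline.

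Overlap between covariate and factor is not avoided elsewhere. UAS7 is the sum of ISS7 and HSS7, yet the baseline UAS7 and HSS7 subgroup models keep the ISS7 score. The forest plot is meant to show whether the effect is uniform, and its baseline-itch rows would come from a differently adjusted model. What is at stake is some precision in those rows and their comparability with the rest.

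**Working it through.** **1. The plan's own figure.** SAP 1.2 states: "This provides 90% power for statistical significance at the 2-sided 2.5% level within each induction dose comparison versus placebo". Its inputs are an effect of 4.7 points, an SD of 6 and 10% dropout. With 60 and 40 reduced by 10% to 54 and 36:

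- SE = 6 × √(1/54 + 1/36) = 1.291
- 4.7 / 1.291 = 3.64; the critical value at 2-sided 2.5% is 2.24
- Power = Φ(3.64 − 2.24) = 91.9%, or 91.1% with the noncentral t

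This agrees with the stated 90%, so SD 6 and 54 v 36 are used below.

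**2. Assumptions that the documents do not supply.** Baseline ISS7 is normal(14, 4) cut to 8–21. The slope b of ISS7 change on baseline is −0.3, −0.5 or −0.7. A single-visit Week 12 ANCOVA stands in for the MMRM.

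**3. What the split leaves behind.** The within-level baseline SD s is about 1.37 (<13) and 2.07 (≥13). About 63% fall at 13 or above, giving roughly 34 v 23 participants in that level and 20 v 13 below it. Under other truncated normals (location 13–15 with scale 3.5; location 14 with scale 6), the split captures about 60–68% of baseline variance and leaves 32–40% unadjusted.

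**4. Variance of the subgroup treatment difference.** Ratio without v with the score ≈ 36 / (36 − b²s²):

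| Slope | <13 (s² = 1.88) | ≥13 (s² = 4.28) |
|---|---|---|
| −0.3 | 36/35.83 = 1.005 | 36/35.61 = 1.011 |
| −0.5 | 36/35.53 = 1.013 | 36/34.93 = 1.031 |
| −0.7 | 36/35.08 = 1.026 | 36/33.90 = 1.062 |

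That is about 0–3% and 1–6%. The formula ignores the cost of estimating the slope. In a simulation at location 14 and scale 3.5, the gain disappeared at slope −0.3 (ratio of empirical SDs 0.996–0.997) and reached 1.022 for ≥13 at −0.7.

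**5. Chance imbalance, one SD.** Shift = |b| × s × √(1/n₁ + 1/n₂):

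- ≥13: 2.07 × √(1/34 + 1/23) = 0.56 points of baseline, so 0.17, 0.28 and 0.39 points of effect at the three slopes
- <13: 1.37 × √(1/20 + 1/13) = 0.49 points of baseline, so 0.15, 0.24 and 0.34 points of effect

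This is about 0.2–0.4 points.

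**6. Bias and type I error.** In the scale 3.5 simulation, with a true effect of −4.7 in both levels, mean estimates were about −4.7 with or without the score. The interaction test, nominally 5%, rejected in 4.6–4.7% of runs without it and 4.7–4.8% with it.

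**The case against.** The strongest reply is that nothing depends on this. It is one of 16 exploratory factors, stated openly and in advance, and it does not touch the primary analysis, the multiplicity procedure or the sample size. The shift is also small beside the noise. In the ≥13 level the SE of the treatment difference is about 6 × √(1/34 + 1/23) = 1.62, a 95% half-width of about 3.2 points, against a one-SD shift of at most 0.39. All of that stands.

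A reader might infer that the baseline-severity estimates are biased, or that the interaction test is invalid. Neither follows. Under randomisation, within-level imbalance is ordinary sampling error that the unadjusted interval already reflects, and the split still adjusts for imbalance between levels.

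The level-specific ratios also overstate what the reported SEs would show. SAP 4.2.6.2 describes one model with an interaction, so its residual variance is pooled. At slope −0.7 the pooled within-level variance is 0.63 × 4.28 + 0.37 × 1.88 = 3.39, giving 36 / (36 − 0.49 × 3.39) = 1.048.

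Nor is restoring the score wholly free of side effects. SAP 4.2.6.1 reports LS means with the OM option, and SAP 4.2.6.2 promises similar outputs. By default a covariate is held at its overall mean, about 14.2 under the assumed distribution, which nobody in the <13 level can have. Treatment differences are unaffected, but the arm-level LS means would be extrapolations. That objection is sound, and one instruction meets it.

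It does not justify dropping the score. The score and its two-level cut are not linearly dependent, so a model with both can be estimated.

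**Conclusion.** The point holds as a minor one about precision and consistency. One exploratory subgroup model omits a collected baseline score that the primary model and the other 15 subgroup models use. Under the assumed baseline distribution and slopes, the variance of the subgroup difference rises by about 0–3% (<13) and 1–6% (≥13), and chance imbalance moves the estimate by about 0.2–0.4 points (one SD) against a planned effect of 4.7. At the shallow end of the slope range the gain is close to nil. The omission itself is plain from the text; its size rests wholly on those assumptions. The documents do not support a claim of systematic bias, of inflated type I error or of any effect on the primary result.

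**What to change.** In SAP 4.2.6.2, limit the exception to region: *when region is the subgroup factor, it is not also entered as a covariate.* Keep the baseline ISS7 score in the baseline ISS7 subgroup model, beside the <13 / ≥13 factor and its interaction with treatment. Add that arm-level LS means in this model are evaluated at each subgroup's own mean baseline ISS7.

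The cost is one degree of freedom and one LS-means instruction. No new data are needed. The change should be made before unblinding so that it stays prespecified.
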